7.4. Stopping rules (By the Data Safety and Monitoring Committee)

The DSMC shall have authority to stop a research protocol in progress and remove individual human participants from a research protocol. The Data Safety and Monitoring Committee may request enrollment be suspended due to safety concerns.

8. Data analysis and statistical considerations

8.1. Statistical Analysis

The primary endpoint is the clinician-evaluated SFGS. We will compare the pre-post change (at baseline and 4 months) in SFGS between the treatment arms. Statistical analyses will be based on a treatment difference relative to baseline at 4 months in a linear random effects model with: a group difference at baseline, a time (0/1) variable indicating 4 months versus baseline, a group-by-time interaction representing the treatment difference, and a random effect at the subject level.

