This proposal will prospectively assess the social, physical, and emotional recognition function in patients with synkinesis. Next, it will measure the effectiveness of neuromuscular retraining therapy to improve muscle coordination compared to chemodenervation, the more established treatment modality, in a single-blinded, randomized control trial using clinician- and patient-reported outcomes measures. Our hypothesis is that patients undergoing neuromuscular retraining therapy will achieve greater improvement on clinical outcome measures as compared to patients receiving chemodenervation.

In this clinical trial, 36 patients undergoing treatment for synkinesis will be enrolled into one of two treatment arms: chemodenervation or neuromuscular retraining therapy. There are 3 specific aims:

AIM 1: Determine the effect of neuromuscular retraining or chemodenervation on clinician-reported and patient-reported outcomes. The primary outcome measure after four and eight months of treatment will be the clinician-reported Sunnybrook Facial Grading System (SFGS) scored on patient videos by blinded reviewers. Further, we seek to measure the efficacy of treatment with existing patient-reported instruments. We will calculate the correlation of clinician-reported outcome measure changes to changes in patient-reported instruments with treatment, including the widely utilized disease specific Synkinesis Assessment Questionnaire (SAQ) and Facial Clinimetric Evaluation Scale (FaCE), and with two disease non-specific instruments, the Hospital Anxiety and Depression Scale (HADS), and Brief-Illness Perception Questionnaire (BIPQ). We will also measure the efficacy of our clinical intervention with social-perceptual and mental health outcome measurement before and after treatment (AIM 3).

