We will conduct a prospective, randomized, single-blinded control trial of neuromuscular retraining therapy versus patient receipt of chemodenervation. Both treatments are widely practiced in the United States for the treatment of synkinesis, and it is not known if retraining therapy achieves better clinical outcomes as compared to chemodenervation. The study design allows measurement of improvement attributable to each treatment and reduces bias through randomization to each study arm. A video-based single-blinded scoring of outcome measures also reduces bias. The first four months of the protocol will allow comparison of individual treatments to answer this research question; the next four months of the protocol will measure additional changes with dual treatment while patients received both therapies in a pragmatic trial emulating clinical practice.

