2.1. Primary outcome and endpoints

To determine improvement in physical functioning from baseline, we will look at the change on the clinician-reported Sunnybrook Facial Grading System (SFGS). The examination is routinely collected at clinic visits. At each clinic visit, patients will be videotaped as a part of routine care. However, patients in the study will undergo a blinded evaluation and SFGS scoring using the video by trained blinded clinicians not participating in their direct clinical care, to decrease observer bias.

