6.3. Recruitment and consent

The human subjects participating in this study will be recruited from the University of Wisconsin *Facial Nerve Clinic*. After physicians identify eligible patients and introduce available treatments, they will ask if the patient is interested in speaking to a study coordinator. A study coordinator will then offer enrollment in both IRB protocol 2015-0366 and this protocol. In clinics where the study coordinator is not available, patients will be given an information sheet, flowchart, and consent form describing the study during the patient's visit at UWHC and told that the coordinator will call within the week to explain the study.

A participant's decision whether or not to participate will not affect the care received as a patient. Participants will be treated according to the standard of care until consent for the study is obtained. Participants must meet inclusion and exclusion criteria as listed above. Participants will be selected without consideration of socio-economic background, however if their insurance status precludes them from coverage for therapy and/or Botox they will need to pay out of pocket. If they are unwilling/unable to do this, we will not enroll them in the study as their treatment with only the treatment covered by insurance would not be truly random.

Following explanation of the consent form, each potential participant will be given an opportunity to read it thoroughly. Before being allowed to sign the consent form, potential participants also will be given an opportunity to ask questions. The investigator will emphasize the fact that the participant can terminate involvement at any time without any consequences. Once the consent form has been signed, the study pre-treatment procedures will be performed if not already captured in the medical record.

A participant is enrolled prior to treatment and will undergo baseline evaluations. They will be randomized on the day of their initial clinic visit.

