7.3. Participant withdrawals

Participants have the right to withdraw from the study at any time for any reason, either before or after treatment begins. Additionally, any participant may be discontinued from the study at any time at the discretion of the investigator if he or another provider feels it is in the best interest of the participant. If a participant withdraws or is withdrawn from one aim, they may continue to participate in the other aims.

Study participation may be terminated early under the following circumstances:

- (1) the participant does not meet all inclusion criteria and is deemed a screen failure
- (2) the participant meets any of the exclusion criteria and is deemed a screen failure
- (3) the participant does not adhere to protocol requirements (e.g., completing questionnaires, refusing permission to have interview recorded, etc.)
- (4) the participant experiences an AE which in the investigator's opinion requires their withdrawal from the study
- (5) the participant is lost to follow up
- (6) death of the participant

The study team will document the reason(s) for withdrawal of each participant in source documents.

Participants that withdraw or are withdrawn prior to treatment will be replaced. Their pre-treatment data may be used to establish baseline function for comparison. Participants that withdraw from any aspect of the study will continue to be cared for per the standard of care.

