8.2. Sample size and power calculation

Each arm will contain 18 participants, for a total of 36 participants. In previous work, we observed a change from baseline in SFGS of 9.4 with a standard deviation of 7.1 and intra-subject correlation of pre-post measurements of 0.86. Assuming the same standard deviation, a correlation of 0.5, and a loss of follow up of 10%, with a mean treatment difference of 7 points between arms, the planned sample size will provide approximately 80% power.

Patients will be recruited from the Facial Nerve Clinic at the University of Wisconsin Hospitals and Clinics. This is a high-volume tertiary care center with approximately 6 new synkinesis patients per clinic, making our pool of eligible participants approximately 72 patients per year. With an accrual goal of 36 participants within 1 year, we would need to recruit 50% of eligible patients over the year.

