8.3. Analysis of endpoints

To reduce the risk of bias, two Department of Surgery research employees will independently grade videos and photos in a blinded fashion using the Sunnybrook Facial Grading System instrument. Video recordings will be presented in random order to two trained research assistants. Ten percent of samples will be included twice to measure intra-rater reliability. Twenty percent of samples will be re-scored by the other rater to measure inter-rater reliability. [name] will be responsible for rater training prior to the investigation, and during the study [name] will provide independent oversight, ongoing training, and resolution of scoring disagreement. At the conclusion of the study, study biostatistician [name], who generated the randomization sequence, will perform data analysis comparing mean changes between groups and account for participant drop out if necessary.

Our qualitative analysis will proceed concurrently with data collection to allow identified themes to be explored in subsequent interviews. In qualitative research this involves both coding the written transcripts and then modeling the coded data. All team members will analyze the data and look for themes and trends that are emergent from the data. For the pre-treatment interviews, we will employ Conventional Content Analysis¹⁵ which will allow us gain direct information from study participants without imposing preconceived categories or theoretical perspectives. For the post-treatment interviews, we will switch to directed content analysis as the findings from pre-treatment interviews will guide our analysis of post-treatment interviews, while capturing emergent themes that come up in the data. We will establish reliability in our analysis through peer debriefing, triangulation, and expert feedback (through [name]), and member checks. Coded transcripts, the codebook, and descriptions of codes will be maintained using NVivo 11 software (QSR International). As coding evolves, changes will be documented in an audit trail. We will map our findings onto the PROMIS measures; specifically, Social

Functioning and Social Isolation scales, to determine the domains that are important to patients but are not included in current quantitative measures.

9. Risks and benefits of trial participation

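### The primary model is an unadjusted comparison of SFGS change; prespecified adjustment for the baseline SFGS already collected would gain precision without new data

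*Combined protocol and SAP*

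**What the plan says.** Section 8.1 compares the baseline-to-4-month change in SFGS between arms, using a linear random effects model with a subject-level random effect and "a group difference at baseline, a time (0/1) variable indicating 4 months versus baseline, a group-by-time interaction representing the treatment difference". Section 8.3 restates this: the biostatistician "will perform data analysis comparing mean changes between groups". Section 2.1 also defines the primary outcome as change in SFGS.

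No section names baseline SFGS, or anything else, as a covariate. The score is nonetheless available: section 3 and the schedule of activities place SFGS before treatment as standard of care.

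Section 8.2 gives two correlations. Previous work showed a change SD of 7.1 and "intra-subject correlation of pre-post measurements of 0.86". The power statement keeps the SD, lowers the correlation to 0.5, and takes 18 per arm, 10% loss and a 7-point difference to reach approximately 80% power.

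**The concern.** The baseline group term can be mistaken for baseline adjustment. It is the opposite: each arm gets a free baseline mean, so the model does not use the fact that randomisation makes those means equal in expectation. With complete data at two visits, the estimate is the difference in mean change. This amounts to fixing the slope of the 4-month score on baseline at 1. ANCOVA estimates that slope, which under equal variances is r and hence below 1.

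If the arms differ at baseline by chance, the change-score estimate moves by (1 − r) times that difference, and adjustment removes the movement. This is the same benefit as the lower variance, seen in a single trial, and should not be counted twice.

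With 36 patients and planned power of about 80%, precision is scarce. Adopting adjustment after the data are seen would look data-driven, so it has to be written down beforehand.

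**Working it through.** **Inputs.** From 8.2: 18 per arm, 10% loss (16.2 evaluable per arm), difference 7, SD 7.1, r = 0.86 observed and 0.5 assumed. From 1.1: baseline SFGS IQR 47.0 to 67.0. My assumptions: two-sided 5% (8.2 gives no significance level), normal scores, equal variances at both visits.

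**The plan's own figure.** At r = 0.5 the change SD equals the score SD, because 7.1 × √(2 × 0.5) = 7.1, so either reading of the SD gives the same result. SE = 7.1 × √(2/16.2) = 2.495; 7/2.495 = 2.806; power = Φ(2.806 − 1.960) = 80.1%. The stated 80% reproduces. A one-sided 5% test would give 87.7%, so two-sided is the reading that fits. Below I use 16 per arm and the t distribution, which lowers the starting point to 77.0%. That is a difference of method, not an error in the plan.

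**What the planned model estimates.** Fitted to one simulated complete data set, the mixed-model interaction and the difference in mean change were both 5.966, with SE 2.149.

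**Effect of adjustment.** The large-sample variance ratio, ANCOVA to change score, is (1 + r)/2. Estimating the slope with 16 per arm multiplies it by 1 + 1/28.

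- r = 0.86: 0.93, a 7% reduction; then 0.93 × 29/28 = 0.963, about 4%.
- r = 0.5: 0.75, a 25% reduction; then 0.75 × 29/28 = 0.777, about 22%.
- Break-even: (1 + r)/2 × 29/28 = 1 at r = 0.931.

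If 7.1 is the change SD and r = 0.86, the score SD is 7.1/√(2 × 0.14) = 13.4. The IQR in 1.1 gives 20/1.349 = 14.8, which is compatible.

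SE of the change score = change SD × √(2/16), on 30 degrees of freedom; the ANCOVA SE is this times the square root of the net ratio, on 29.

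| Scenario | Change SD | SE, change → ANCOVA | Power, change → ANCOVA |
|---|---|---|---|
| A: r 0.86, score SD 13.4 (observed) | 7.1 | 2.51 → 2.46 | 77.0% → 78.4% |
| B: r 0.5, score SD 7.1 | 7.1 | 2.51 → 2.21 | 77.0% → 86.4% |
| C: r 0.5, score SD 13.4 (sensitivity) | 13.4 | 4.74 → 4.18 | 29.8% → 36.7% |

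Simulation with 100,000 trials per scenario agreed: power 76.8% → 78.3%, 77.1% → 86.4% and 29.9% → 36.9%, with Type I error 4.9% to 5.0% for both methods. By the normal approximation used for the plan's 80.1%, adjusted power is 82.9% at r = 0.86 and 90.0% at r = 0.5.

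**Chance imbalance.** With 18 per arm, a one-SE baseline difference is score SD × √(2/18), or 4.5 points in A. It shifts the change-score estimate by (1 − r) times that difference: 0.14 × 4.47 = 0.6 points in A, 0.5 × 2.37 = 1.2 in B, 0.5 × 4.47 = 2.2 in C.

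**Dropout.** Take 18 per arm at baseline and 16 at 4 months, in A, with variances treated as known:

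- Planned model: √(2 × 13.42² × [(1 − 0.86²)/16 + 0.14²/18]) = 2.50.
- Common-baseline mixed model: √(2 × 13.42² × (1 − 0.86²)/16) = 2.42.
- Completers' ANCOVA on the same footing: 2.51 × √0.93 = 2.42. The 2.46 in the table also carries the cost of estimating the slope.

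Patients with only a baseline score therefore add little to the treatment contrast, and the two adjusted analyses should perform almost alike.

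**The case against.** The strongest reply is that the gain is negligible where the documents have data. The observed r of 0.86 and change SD of 7.1 fit the baseline IQR, and there adjustment brings 1.4 power points. Scenario B needs a score SD about half of what the IQR suggests. Scenario C combines an SD implied by one correlation with a different correlation, and its low power is a sample-size matter, not a result of omitting adjustment. Much of this stands: A is the best-documented case, B shows what the plan's own correlation would imply, and C is only a sensitivity case.

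It does not remove the point. The previous work appears to be the retrospective cohort in 1.1 (same mean change and SD), scored by the clinic's own team and described there as subject to bias. The trial uses blinded video raters and adds a second treatment, so r may differ, and the plan itself chose 0.5. The downside is slight, since ANCOVA stops helping only above about r = 0.93.

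It is also fair to say that adjustment is not literally free: it spends one degree of freedom, and section 12.6 requires written IRB approval for protocol changes. Nor is the order of baseline and assignment undocumented. Section 7 places assignment after the clinical evaluation, and 5.3 withholds it until after consent. What remains open is narrower: 6.3 says that after consent "the study pre-treatment procedures will be performed if not already captured in the medical record", so a baseline video recorded after assignment is not ruled out.

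**Conclusion.** The point holds as a suggestion to consider. The planned analysis is valid and unbiased; with complete data it is the unadjusted difference in mean change, and no section plans adjustment for the baseline SFGS already collected. Under normality, equal variances, 16 evaluable per arm and a two-sided 5% test, adjustment cuts the variance by about 4% at r = 0.86 (1.4 power points) and about 22% at r = 0.5 (about 9 power points in B, 7 in C), with Type I error unchanged. The size is uncertain because the trial's own r is unknown; the direction is not in doubt below about r = 0.93.

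A separate, minor wording point: AIM 1 in the Summary attaches the primary outcome to both four and eight months, whereas 8.1 tests only 4 months and 1.1 says "The first four months of the protocol will allow comparison of individual treatments to answer this research question".

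**What to change.** In 8.1, prespecify a baseline-adjusted comparison of 4-month SFGS with small-sample degrees of freedom, in one of two forms.

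1. **ANCOVA** of 4-month SFGS on arm and baseline SFGS. The treatment effect is the same whether the outcome is the 4-month score or the change, so the endpoint in 2.1 can stay.
2. **The mixed model with a common baseline mean**, that is, without the baseline group term. This keeps patients who have only a baseline score, but assumes equal baseline means. So first state that the baseline SFGS video is recorded before assignment is revealed, and how replaced patients are handled, since 7.3 says "Participants that withdraw or are withdrawn prior to treatment will be replaced". If that cannot be assured, use ANCOVA on the pre-treatment score.

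Baseline SFGS should not be added as a covariate to the existing model, where it is already an outcome row. Change the description in 8.3 to match. As a minor alignment, make 4 months the single primary time point in AIM 1 and 8 months secondary.

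The cost is amended text, with the IRB approval that 12.6 requires. No new data, visits or patients are needed.

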Participants will be primarily identified from our University of Wisconsin *Facial Nerve Clinic*. While most patients with facial nerve paralysis recover in 3 months, patients with chronic facial paralysis may still benefit from spontaneous recovery of muscle function thereafter. Symptoms of synkinesis are often not displayed until 4 months with the display of aberrant facial muscle motions. Eligible patients will demonstrate synkinesis and had their onset of peripheral facial paralysis from any cause at least 4 months prior. Muscle function and synkinesis will be assessed using standard clinical evaluation tools.

Exclusion criteria: (1) under 18 years of age (2) previous treatment with reanimation surgery (except for those patients who underwent upper eyelid weight placement to aid in eye closure), (3) intolerance or contraindication to botulinum toxin injection, and/or (4) previous treatment for synkinesis with chemodenervation or neuromuscular retraining therapy (5) vulnerable populations such as known prisoners, pregnant/breastfeeding women, or subjects with impaired decision-making capacity, including those with severe psychiatric illnesses (6) individuals over 89 years of age

Pre-Treatment Screening and Testing: Pre-treatment activities will include clinical evaluation and clinician- and patient-reported instruments that are already standard of care (SFGS, SAQ, FaCE), a semi-structured interview, and the tasks included in IRB Protocol 2015-0366. Patients will be randomly assigned to one of two treatments; Arm 1: neuromuscular retraining therapy for four months, with chemodenervation added thereafter, or Arm 2: Botox/chemodenervation for four months, with neuromuscular retraining therapy added thereafter. Allocation schedule will not be known to clinicians prior to consenting.

Blinding: Research team members who will score the videos will be blinded. The physician conducting the initial clinic visit will be blinded to the patient's treatment arm until after they have been enrolled. The physician providing treatment, interviewer, and study coordinator will not be blinded to the participant's treatment arm.

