5.3. Allocation to intervention

Participants will be randomized to each treatment arm with equal probability (1:1 randomization) using a computerized random number generator with random block size (all study personnel except the statisticians are blinded to block size). The randomization assignment will be revealed to the unblinded study coordinator after consent. The clinicians will be blinded to the treatment until the end of clinic.

6. Participant recruitment and consent

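### The primary model is an unadjusted change-score comparison: valid on average, but it leaves precision unused and does not correct chance imbalance in time since onset

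*Combined protocol and SAP*

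**What the plan says.** Section 8.1 states the primary comparison as "We will compare the pre-post change (at baseline and 4 months) in SFGS between the treatment arms". The model contains "a group difference at baseline, a time (0/1) variable indicating 4 months versus baseline, a group-by-time interaction representing the treatment difference", plus a random effect for subject. It has no other covariate. Section 8.3 adds only that mean changes will be compared and drop-out accounted for if needed.

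Section 5.3 describes 1:1 allocation "using a computerized random number generator with random block size" and names no stratification factor.

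On time since onset, section 4.1 requires at least four months since paralysis from any cause and sets no upper limit. Section 3 remarks that "patients with chronic facial paralysis may still benefit from spontaneous recovery of muscle function thereafter", where the point of reference is the usual three-month recovery. Section 1.1 faults many earlier therapy studies, done in the early months of paralysis, for not controlling for spontaneous recovery.

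On size, section 8.2 says "Each arm will contain 18 participants, for a total of 36 participants". It reports an earlier result ("we observed a change from baseline in SFGS of 9.4 with a standard deviation of 7.1", with a pre-post correlation of 0.86), then assumes the same SD, a correlation of 0.5, 10% loss and a 7-point difference, and claims about 80% power.

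**The concern.** Patients a few months past onset may still be improving on their own, while patients years past onset are less likely to be. The outcome is SFGS change over four months, so any such improvement enters it directly. The baseline group term and the subject effect absorb stable differences in SFGS level. They do not absorb differences in the rate of change. If recent-onset patients fall unevenly between two arms of 16 to 18, part of the estimated treatment difference reflects that imbalance.

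The second loss is more general. A change score fixes the coefficient of baseline SFGS at 1 instead of estimating it. When the pre-post correlation is moderate, as section 8.2 assumes, that wastes precision in a trial whose power is already at the usual minimum.

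**Working it through.** **Inputs.** From section 8.2: 18 per arm, 10% loss (18 × 0.9 = 16.2), difference 7, SD 7.1, correlation 0.5 assumed and 0.86 observed. Assumed: two-sided alpha 0.05 (not stated in the plan), and r, the correlation between time since onset and SFGS change (not given), taken over 0 to 0.5.

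**1. The plan's own figure.** SD of change = 7.1 × √(2(1 − 0.5)) = 7.1. The normal approximation at 16.2 per arm gives 80.1%, so the stated 80% reproduces. The noncentral t at 16 per arm gives 77.0%, which is the reference below.

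**2. Baseline SFGS alone.** ANCOVA residual SD = raw SD × √(1 − ρ²), with the SD of change held at 7.1.
- ρ = 0.5: raw SD 7.1; residual SD 7.1 × √0.75 = 6.15; simulated power about 86%.
- ρ = 0.86: raw SD 7.1/√0.28 = 13.4; residual SD 13.42 × √(1 − 0.7396) = 6.85; simulated power about 78-79%.

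**3. Chance imbalance in onset time.** The between-arm difference in a standardised covariate has SD √(2/16) = 0.35. It exceeds 0.5 SD in about 16% of trials, and its 95% limit is 1.96 × 0.354 = 0.69. The resulting shift in the unadjusted estimate is r × 7.1 × imbalance.
- r = 0.2: 0.2 × 7.1 × 0.693 = 0.98 points.
- r = 0.5: 0.5 × 7.1 × 0.693 = 2.46 points.

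These are 14% and 35% of 7. The average absolute shift is smaller, at 0.4 and 1.0 points.

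**4. Onset time added to the change-score model.** Simulated power at 16 per arm, allowing for the cost of estimating the covariate:

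| r | Unadjusted | Adjusted |
|---|---|---|
| 0 | 77% | 75.5% |
| 0.1 | 77% | 76% |
| 0.2 | 77% | 77% |
| 0.3 | 77% | 79% |
| 0.5 | 77% | 86% |

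**5. Behaviour when imbalance occurs.** Overall, unadjusted type I error stays at about 5%. Among trials with an imbalance above 0.5 SD it is about 5% (r = 0.1), 7.5% (r = 0.3) or 12.5% (r = 0.5). When the imbalance runs against the better arm, unadjusted power is 72%, 59% or 43%, and adjusted power is about 72%, 76% or 84%. Adjusted type I error stays near 5% throughout.

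**6. Which term does the work.** In one simulated complete data set with a true difference of 7, the planned model estimated 4.20. Adding onset time as a main effect left it at 4.20. Adding its interaction with time moved it to 6.88.

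**The case against.** The strongest reply is that nothing here is invalid. Randomisation protects the unadjusted test, and chance imbalance in any covariate is already part of its standard error (7.1 × √(2/16) = 2.51 points). The SD of 7.1 comes from a cohort that also started at least four months after onset, so it already contains spread from onset time. This stands. A reader might infer that the planned estimate is biased or its error rate inflated. On average over randomisations neither is so.

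A reader might also infer that the protocol treats onset time as driving recovery. It says only that patients may still recover, and its criticism of earlier studies concerns the early months. The four-month floor with demonstrated synkinesis is a partial control, and both arms run concurrently. No section says recovery varies with onset time beyond four months, so r could be close to zero.

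It is also tempting to put the reduced SD into a two-sample formula and report 79-88% power for r of 0.2-0.5. That leaves out the cost of estimating the covariate; simulation gives 77-86%.

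Finally, a sparse model is defensible with 32 to 36 patients, and cause, age and severity are arguable covariates too. That argues against a long covariate list. It is a weak argument against baseline SFGS, whose correlation with the outcome section 8.2 itself supplies.

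**Conclusion.** The concern holds as one of precision and of imbalance in the trial actually drawn, not of validity. The firmer gain is from baseline SFGS: 77% to about 86% at the plan's assumed correlation of 0.5, but only to 78-79% at the observed 0.86. The gain from onset time depends on r, which the documents do not give: none at 0.2, about 2 points at 0.3, about 9 at 0.5, and a loss of 1-1.5 points at 0-0.1. Its further value is protection against a 1.0-2.5 point shift at the 95% limit of imbalance (r of 0.2-0.5).

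All figures take 7.1 as the SD of change, 16 per arm and two-sided 0.05. The change is worth making before any outcome is seen, because an adjustment chosen after imbalance appears in the baseline table would be open to doubt.

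**What to change.** In section 8.1, pre-specify the primary analysis as ANCOVA of 4-month SFGS on arm, baseline SFGS and log months since onset. The log suits a range with no upper limit.

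If the mixed model is kept, add log months and its interaction with time; the main effect alone does not adjust the change. Do not also enter baseline SFGS as a covariate there, because it is already an outcome row.

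State that the ANCOVA is a different estimator from the planned model. It conditions on baseline, whereas the planned model reproduces the change-score comparison. Leave the randomisation unstratified, which is reasonable with 36 patients.

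Cost: a short edit; two degrees of freedom for the ANCOVA (30 to 28 with 32 patients); 1-1.5 points of power from the onset term if r is 0-0.1; and recording the onset date itself. Eligibility needs only a check against the four-month threshold, so an exact date is likely to be held but the documents do not confirm it.
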